3.8.4. Overall outcomes

Overall outcomes by the end of the study period (discharge from outpatient care/lost to follow-up/dead/under on-going active follow-up) and follow-up durations will be recorded. Any deaths encountered during follow-up will be recorded. The medical records for patients who are discharged will also be examined for mortality data.

3.9. Data quality assurance

An e-learning module will be prepared by the study team. This will contain the data collection guides and video manual. Upon completion, each study investigator will need to undergo a five-item assessment. An iterative process in which investigators have to redo the assessment or module will dictate their progress as follows:

- An assessment percentage of 100% will indicate successful completion of the module, which will allow the investigator to collect data for the study
- An assessment percentage less 100% will require repeating the assessment

- Five attempts will be allowed
- Subsequent failed attempts will entail review of the module components again

3.10. Planned statistical analysis

3.10.1. External validation

Using IMPACT, the five- and ten-year estimated risk of disease progression for every patient included in this cohort study will be calculated. Kaplan-Meier method will be used to obtain the observed risks. The predictive performance of IMPACT will be assessed by examining measures of calibration and discrimination. Calibration refers to how closely the predicted 5- and 10-year risk of progression agrees with the observed risk. A calibration plot compares the observed and predicted rates of events for each group. A perfect match indicates accurate calibration. The Brier score for censored survival data will also be calculated, which is a measure of accuracy and is the average squared deviation between predicted and observed risk; a lower score represents greater accuracy. Discrimination is the ability of the risk score to differentiate between those patients who do and those who do not experience disease progression during the study timeframe. This measure is quantified by calculating the C-statistic, D-statistic and Chambless and Diao's time-dependent AUC (area under the receiver operating characteristic curve [ROC]) which are tailored towards censored survival data. Model assumptions will be tested by examination of Schoenfeld residuals, and influential observations will be examined using DFBETA panels.

The effect of patient age, comorbidity, and performance status on the risk of disease progression and intervention will be assessed using a competing risk analysis. Patients will be split based on WHO PS into two categories: 0-1 and 2-4 and stratified by ACCI (Table 1) into three groups: 0-2, 3-5 and ≥ 6 . An ACCI score of ≤ 2 corresponds to patients who are young (<60 years) with few or no comorbidities. An ACCI score of 3–5 corresponds to either an older patient with few comorbidities, or a younger patient with several comorbidities, and an ACCI score ≥ 6 denotes older patient with comorbidities (24).

Two competing risk analyses will be performed. One assessing the cumulative incidence rate (CIR) of primary intervention at different time points following diagnosis stratified by PS and ACCI groups and the other will evaluate the CIR of disease progression. The competing event for the former will be non-meningioma-specific mortality either observed during follow-up or after being discharged from outpatient care. Patients who remain under follow-up will be censored at the last outpatient clinic appointment. Patients discharged alive from outpatient care will be censored at the last time they were seen by a healthcare physician up to the date of data entry.

For the disease progression analysis, mortality after hospital discharge could not be used as a competing event as the time interval between discharge and death could have seen radiological changes which meet the disease progression definition. Instead, four events will

be considered competing in nature, discharge from outpatient care, loss to follow-up, death during follow-up or an intervention before disease progression occurred with the first three grouped together. Censoring will only be done for patients who remain under follow-up at the last clinic appointment. To test the equality across CIR groups, the Fine and Gray test will be carried out. Plots of CIRs and 95% confidence intervals (CIs) will also be generated and compared to the training data set (11).

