- To recalibrate the prognostic model IMPACT
- To determine the growth patterns of incidental meningiomas
- To examine the MRI and pathology features of meningiomas subject to surgical resection
- To determine the risk of post-intervention complications and tumour recurrence/growth for meningiomas subject to surgery, stereotactic radiosurgery, or fractionated radiotherapy
- To assess the economic implications of stratifying follow-up according to risk of disease progression

Study design Retrospective study of longitudinal radiological and clinical outcomes of incidental intracranial meningioma patients at participating centres diagnosed between 01/01/2009 and 31/12/2010. Data will be recorded until death or last date of follow-up.

Sample size 1500 patients

STUDY FLOWCHART

[figure not shown]

TABLE OF CONTENTS

STUDY SYNOPSIS	3
STUDY FLOWCHART	4
1 INTRODUCTION	6
1.1. THE IMPACT MODEL	7
2 OBJECTIVES	7
2.1. Primary objective	7
2.2. Secondary objectives	7
3 METHODS	7
3.1. Study design	7
3.2. Study population and eligibility criteria	7
3.3. Patient identification	8
3.4. Sample size	9
3.5. Study endpoints	9
3.6. Data collection	9
3.7. REDCap database	9
3.8. Recorded variables	10
3.9. Data quality assurance	13
3.10. Planned statistical analysis	14
4 ETHICS AND DISSEMINATION	16
4.1. Study registration	16
4.2. Local investigator responsibilities	16
4.3. Confidentiality and data protection	16
4.4. Ownership	17
4.5. Dissemination of results	17
4.6. Authorship eligibility	17
5 FUNDING	17
6 STUDY TIMELINE	18
7 CONCLUSION	18
8 REFERENCES	18
9 APPENDICES	20

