3.4. Sample size

For external validation studies, a minimum of 100 events is required (12). The risk of incidental meningioma progression is estimated to be 10% (11). Based on this, data for 1000 patients will be required. To account for variability in the progression risk, follow-up regimes and loss to follow-up, we will include a minimum of 1500 patients across participating centres.

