3.10.2. Model recalibration

If calibration and discrimination measures of external validation demonstrate a poor fit, the model will be recalibrated and adjusted using the data of included patients. This will be done over four stages:

- Stage 1: The regression coefficients (including the intercept and slope) will be recalibrated. This will be done using a logistic regression model fitted with the linear predictor as the only covariate.
- Stage 2: The recalibrated model predictors will each be removed in a stepwise manner by a non-automated criterion-based procedure starting with the variable with a hazard ratio closest to 1. After removal of this variable, the aforementioned measures of discrimination of calibration and discrimination will be reassessed to detect model improvement. If the performance of the model is unimproved or worsens, the variable will be reintroduced to the model. This step will be repeated in a staged manner until no further improvements are detected. Introduction of new predictive variables will not be possible as data points captured in this study have been limited to predictive parameters and outcomes as per the IMPACT model.
- Stage 3: The internal validity of the updated model will be assessed using a bootstrapping method
- Stage 4: Adjusted stratification by ACCI and PS (Table 1) will be performed to achieve statistically significant differences in equality across cumulative incidence rate groups, judged by the Fine and Gray test

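### Calibration of IMPACT is judged on point estimates and an unscaled Brier score, and poor fit then starts a fixed four-stage update, not the smallest one the data support

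*Protocol*

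**What the plan says.** Section 3.10.1 computes each patient's 5- and 10-year risk from IMPACT and takes observed risks from Kaplan-Meier estimates. Calibration is examined on a plot comparing the two by group, with the comment "A perfect match indicates accurate calibration". A Brier score for censored data is added, with the guide that "a lower score represents greater accuracy". Discrimination is measured by the C-statistic, the D-statistic and a time-dependent AUC. Confidence intervals are mentioned only for the cumulative incidence plots later in the same section.

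Section 3.10.2 opens with the condition "If calibration and discrimination measures of external validation demonstrate a poor fit" and then sets out one sequence:
- Stage 1 re-estimates intercept and slope by logistic regression on the linear predictor.
- Stage 2 removes predictors one at a time, and puts a predictor back if performance is no better or is worse.
- Stage 3 bootstraps the updated model.
- Stage 4 redraws the ACCI and performance-status strata so that the cumulative incidence groups differ significantly.

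Section 3.10.3 refers to this text as the statistical analysis plan and says it will be reviewed before the final analysis.

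**The concern.** The primary objective is to validate the model externally. A reader of the calibration results needs to know how far observed risk may lie from predicted risk by chance alone. A grouped plot without intervals does not show that, and a raw Brier score at a low event risk barely separates an informative model from an uninformative one. The calibration slope enters only as Stage 1 of the update, after fit has been judged poor, and not as a validation result.

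The update is also out of proportion to the most ordinary kind of miscalibration. If the new centres simply have a higher or lower baseline risk, correcting that one quantity is enough. As written, the sequence does not stop there. It goes on to drop predictors on apparent performance with no minimum gain, and to redraw strata with statistical significance as the target. Both steps let chance features of this cohort into the revised model.

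**Working it through.** **Plan's own figure.** Section 3.4 takes 100 events and a 10% progression risk: 100 / 0.10 = 1000, which agrees with "Based on this, data for 1000 patients will be required". The enlarged target is given by "we will include a minimum of 1500 patients across participating centres". At 10% this yields 1500 × 0.10 = 150 events, and 100 events are still reached if the risk falls to 100 / 1500 = 6.7%. The 10% has no stated time horizon.

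**Assumptions.** Section 1.1 names three risk groups, but the protocol gives neither their sizes nor their risks. Two mixes with an overall risk of 10% are used, at one horizon and without censoring:
- Mix A: 3 / 12 / 28.7% in 50 / 35 / 15% of patients.
- Mix B: 3 / 8 / 19% in equal thirds.

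**Sampling error on the plot.** The 95% half-width for a group is 1.96 × √[r(1 − r)/n]. At 1500 patients:
- Mix A (n = 750, 525, 225): 1.2, 2.8 and 5.9 percentage points.
- Mix B (n = 500 each): 1.5, 2.4 and 3.4 points.

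Censoring widens these. The observed/expected (O/E) ratio summarises the same uncertainty. For a correct model its approximate 95% interval is exp[±1.96 × √(0.9/E)]:
- E = 100: 0.83 to 1.20.
- E = 150: 0.86 to 1.16.

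**Brier score.** The expected score is Σ share × [r(1 − r) + (r − predicted)²].
- Everyone given 10%: 0.10 × 0.90 = 0.090.
- Mix A, correct model: 0.5 × 0.0291 + 0.35 × 0.1056 + 0.15 × 0.2045 = 0.0822; scaled Brier 1 − 0.0822/0.090 = 8.7%.
- Mix B, correct model: (0.0291 + 0.0736 + 0.1539)/3 = 0.0855; scaled Brier 5.0%.
- Calibrated Cox model, assumed linear-predictor SD of 1.0 (AUC about 0.77): 0.0796; scaled Brier 1 − 0.0796/0.090 = 11.6%.
- Mix A with every predicted risk halved: 0.0822 + 0.5 × 0.015² + 0.35 × 0.06² + 0.15 × 0.143² = 0.087.

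The last line has a true O/E of 2.0, yet its Brier score is still below that of the uninformative model. Without the 0.090 alongside, none of these values can be read as good or bad.

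**Discrimination.** For a model with no information the C-statistic is about 0.50, with standard error about 0.030 at 100 events and 0.025 at 150 (Hanley-McNeil). The C-statistic depends only on ranking, so halving all risks leaves it unchanged.

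**Update sequence.** Section 3.10.2 contains no step that asks whether correcting the baseline risk alone, or baseline and slope, already suffices. Predictor removal follows Stage 1 without such a check.

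**The case against.** The strongest reply is that the perfect-match remark explains how to read the plot and is not a pass/fail rule. The same paragraph defines calibration by degree of agreement. That is right. A reader might infer that a valid model would usually be declared miscalibrated, but the text does not support this. It never says that anything short of a perfect match is failure. In simulation at 1500 patients (one horizon, no censoring), a correct model lies within 3 points in all three groups in 67% (mix A) to 91% (mix B) of studies.

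A reader might also infer that a useless model could pass. A constant 10% prediction shown in three arbitrary groups of 500 does lie within 3 points in all of them 94% of the time, but the planned C-statistic, D-statistic and AUC would expose it.

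The Brier guide is correct when models are compared on the same patients and horizon. The grouped plot would reveal risks halved throughout, even though the Brier score does not. Stage 2 restores predictors that do not help, and Stage 3 checks the updated model by bootstrap. All this stands and limits the point. What remains is that Stage 2 asks for no minimum improvement, and that Stage 3 is not said to repeat the removal steps within each bootstrap sample.

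If the trigger needs poor calibration and poor discrimination together, a pure baseline shift would not start the update at all. It would then go uncorrected, so neither reading yields the proportionate update.

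The numerical meaning of poor fit may properly be settled in a later analysis plan, and its absence alone would not be a finding.

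**Conclusion.** The point holds as an improvement to methods the protocol itself states. Calibration is judged by grouped point estimates and an unscaled Brier score, without intervals. At 10% risk the Brier score separates an uninformative model (0.090) from a correctly calibrated one (about 0.080 to 0.086) by only 0.004 to 0.010. The update that follows poor fit is a fixed run and does not select the smallest adequate change.

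The 0.090 follows from the protocol's 10%. The other Brier values and the group half-widths rest on assumed risk distributions, one horizon and no censoring. The documents do not support a claim that the plan would usually reject a valid model or accept a worthless one. The synopsis objective "To recalibrate the prognostic model IMPACT" omits the condition given in sections 2.2 and 3.10.2; this is a matter of wording and carries no weight here.

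**What to change.** **Section 3.10.1.** At 5 and 10 years, report the O/E ratio and a calibration slope from a survival model that handles censoring, each with a 95% confidence interval. Add a smoothed calibration curve with a confidence band. Report the Brier score scaled to the covariate-free risk estimate, 1 − Brier/Brier of that estimate. Read these together with the planned C-statistic, D-statistic and AUC.

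**Section 3.10.2.** Replace the automatic four-stage run with a choice among no update, baseline risk only, baseline plus slope, and coefficient revision, made by a closed test sequence that controls the overall error rate. Separate unadjusted intervals should not serve as the trigger: four of them (O/E and slope at two horizons) would flag a correct model in 1 − 0.95⁴ ≈ 19% of studies if independent. Carry out predictor removal and regrouping by ACCI and performance status only if the simpler updates are rejected.

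**Cost.** Revised wording and a modest amount of extra analysis, with no further patients or data items. The downside is that the model will be revised less often.

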For patients discharged from outpatient care, data sources will be checked for any readmissions/rescans thought to be attributed to the incidental meningioma within the study timeframe; date of diagnosis up to the date of data entry. Outcome following readmissions/rescans will be noted.

Grade I	Any non–life-threatening deviation from normal postoperative course, not requiring invasive treatment
Grade Ia	Complication requiring no drug treatment
Grade Ib	Complication requiring drug treatment
Grade II	Complication requiring invasive treatment such as surgical, endoscopic, or endovascular interventions
Grade IIa	Complication requiring intervention without general anaesthesia
Grade IIb	Complication requiring intervention with general anaesthesia
Grade III	Life-threatening complications requiring management in ICU
Grade IIIa	Complication involving single organ failure
Grade IIIb	Complication involving multiple organ failure
Grade IV	Complication resulting in death
Surgical Complications	Adverse events that are directly related to surgery or surgical technique
Medical Complications	Adverse events that are not directly related to surgery or surgical technique
Suffix “T” (Transient)	New neurologic deficit improving within 30 days of surgical procedure; can be added to each grade of complication
Suffix “P” (Persistent)	New neurologic deficit extending beyond 30 days of surgical procedure; can be added to each grade of complication

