Scan date (at progression or last follow-up date if no progression)	DD/MM/YYYY	Required
WHO PS at time of progression/last follow-up	Dropdown list/checkbox 
 • 0 • 1 	Required. Allow one option only

	
 • 2 • 3 • 4 • 5 (dead) 	
fRT (SECTION/PAGE 8)		
Pre-radiation WHO PS	Dropdown list/check box 
 • 0 • 1 • 2 • 3 • 4 	Required entry
Pre-radiation comorbidity	Check box 
 • Myocardial infarction • Congestive heart failure • Peripheral vascular disease • Hemiplegia • Cerebrovascular disease • Pulmonary disease • Diabetes • Renal disease • Liver disease • Peptic ulcer disease • Cancer • Dementia • Connective tissue disease • AIDS • Hypertension • Skin ulcers/cellulitis • Depression • On Warfarin 	Required entry. Allow multiple options. Note to data collector: Age and comorbidities will be used to calculate the age adjusted Charlson comorbidity index. Each of these is defined in the guide provided
Number of fractions	Free field	Required entry
Fractionated dose	Free field	Required entry
Total dose	Free field	Required entry
Early CTCAE toxicity (≤3 months)	Checkbox	Required entry
Toxicity	Free field	Prompt entry if previous option (Early CTCAE toxicity (≤3 months)) is ticked

		Note to data collector: https://ctep.cancer.gov/protocoldevelopment/electronic_applications/ctc.htm Use the following format: System class organ (SOC)-CTCAE term-grade e.g. nervous system disorders-headache-1. Select the complication with the highest toxicity grade
Late CTCAE toxicity	Checkbox	Required entry
Toxicity	Free field	Prompt entry if previous option (Late CTCAE toxicity) is ticked Note to data collector: https://ctep.cancer.gov/protocoldevelopment/electronic_applications/ctc.htm Use the following format: System class organ (SOC)-CTCAE term-grade e.g. nervous system disorders-headache-1. Select the complication with the highest toxicity grade
Meningioma progression/regrowth	Checkbox	Required
Scan date (at progression or last follow-up date if no progression)	DD/MM/YYYY	Required
WHO PS at time of progression/last follow-up	Dropdown list/checkbox 
 • 0 • 1 • 2 • 3 • 4 • 5 (dead) 	Required. Allow one option only
Discharge from outpatient care/Lost to follow-up (SECTION/PAGE 9)		
Date of data entry into the database	DD/MM/YYYY	Required entry

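### In the intervention competing-risk analysis, discharged patients who die are followed to death but survivors are censored at last physician contact, so follow-up depends on outcome

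*Protocol*

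**What the plan says.** Protocol 3.10.1 plans two competing-risk analyses, one for primary intervention and one for disease progression. This point concerns the first.

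- **Competing event:** "The competing event for the former will be non-meningioma-specific mortality either observed during follow-up or after being discharged from outpatient care".
- **Censoring after discharge:** "Patients discharged alive from outpatient care will be censored at the last time they were seen by a healthcare physician", with data entry as the latest possible date.
- **Patients still followed:** "Patients who remain under follow-up will be censored at the last outpatient clinic appointment".
- **Search for deaths (3.8.4):** "The medical records for patients who are discharged will also be examined for mortality data".
- **Search for later treatment (3.8.3):** for discharged patients, "data sources will be checked for any readmissions/rescans thought to be attributed to the incidental meningioma within the study timeframe", a period that runs to data entry. Page 9 of the form (Appendix 1) routes a rescan to surgery, SRS or fRT where one follows.
- **Dates on page 9:** it holds "Date of data entry into the database", and a Dead/Alive item that appears only when the rescan box is not ticked. As shown, it has no field for the date last seen.
- **Cause of death (page 10):** meningioma-related and unrelated deaths are recorded separately. In the intervention analysis a meningioma death is neither the event nor a competing event, and no censoring rule covers it.

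**The concern.** Take two patients discharged at the same visit, whose records are searched on the same later date. If the search finds a death, the patient stays in the risk set until the date of death. If it finds the patient alive and untreated, the patient leaves the risk set at the last physician contact, possibly years earlier. The same search thus lengthens follow-up for those with an event and not for those without, and late events are divided by a depleted risk set.

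The intervention curves are to be compared across PS and ACCI groups and with the training data. If frailer or older patients are discharged earlier or more often, the distortion will differ between the groups and may look like an effect of PS or ACCI.

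Separately, a patient who dies of the meningioma untreated can no longer receive an intervention. If such a death is handled as censoring, that patient is treated as someone who might still be treated.

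**Working it through.** **Plan's own figure.** The protocol gives no figure on this point. Its only derived figure, the sample size, reproduces (100 / 0.10 = 1000) but has no bearing here.

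**Direction.** The Aalen-Johansen estimate for event type k can be written

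CIF_k(t) = (1/N) × Σ 1/G(T_i−), summed over type-k events up to t,

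where G is the Kaplan-Meier estimate of remaining uncensored. Censoring only event-free patients earlier keeps every counted event and lowers G, so each event gets a larger weight. For given captured data, both curves in this analysis (intervention and non-meningioma death) can only rise. Turning meningioma deaths into censorings acts the same way.

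**Size: inputs.** Diagnosis in 2009-2010 is from Protocol 3.1. Data entry 10-12 years after diagnosis is an assumption. The documents give no rates, so these are assumed, per year: intervention 2% before and 0.5% after discharge, non-meningioma death 3%, meningioma death 0.2%, discharge 15%. All post-discharge interventions are captured. I simulated 400,000 patients per scenario and compared the written rule (meningioma deaths censored) with a common cut-off at data entry and any death competing.

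| Last physician contact | Intervention, 10 years: written vs common | Excess | Non-meningioma death, 10 years: written vs common | Excess |
|---|---|---|---|---|
| Discharge visit | 16.2% vs 10.4% | 5.8 | 40.1% vs 23.9% | 16.2 |
| About 5 years before data entry | 12.3% vs 10.4% | 1.9 | 30.1% vs 24.1% | 6.0 |
| About 1 year before data entry | 10.8% vs 10.5% | 0.3 | 24.9% vs 23.9% | 1.0 |

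**Range.** I varied non-meningioma death over 1, 3 and 10% and post-discharge intervention over 0, 0.5 and 2% per year. The 10-year excess was:

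- last contact at discharge: about 1-13 points for intervention, 6-18 for death;
- last contact about 1 year before data entry: about 0.1-0.7 points for intervention, 0.3-1.6 for death.

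**Which part matters.** In the first row of the table, the discharge rule alone gives 15.9% for intervention (15.9 − 10.4 = 5.5 points). Censoring meningioma deaths alone gives 10.5% (0.1 points). With meningioma death varied over 0.05-0.5% per year, the second part adds about 0.1-0.6 points.

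**Missed interventions.** With last contact at discharge, 3% death and 2% post-discharge intervention per year, the true 10-year intervention figure is 15.6%. The written rule gives 18.8% if half of the post-discharge interventions are captured and 12.9% if none are. At 10% death the true figure is 11.6%, and the rule gives 11.3% and 8.1%. The net error can therefore fall below the truth.

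**Groups.** Take two groups with the same rates (intervention 2%, death 4% per year throughout), full capture, last contact on average 2 years after discharge, and discharge at 5% or 33% per year. The true 10-year intervention figure is 15.0% in both. The written rule gives 16.5% and 24.3%, a spurious difference of 24.3 − 16.5 = 7.8 points.

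**The case against.** The strongest reply is that the rule is close to harmless. Last contact may be with any physician, not only the neurosurgical clinic, and may fall at any time up to data entry. In an older cohort with comorbidity it could often be recent, and the intervention excess is then a fraction of a point. This stands as a limit on size. It does not remove the fault, because nothing in the protocol ensures recent contact and the form as shown does not record it.

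A reader might infer that both planned cumulative incidences are overstated. The documents do not support that. In the progression analysis, discharge, loss to follow-up and death during follow-up are themselves competing events, so this asymmetry does not arise. The second curve affected is non-meningioma death within the intervention analysis.

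A reader might also infer that the intervention curve must end above the truth. That needs complete capture of treatment after discharge, whereas the protocol searches only for readmissions and rescans attributed to the meningioma.

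Nor is this a fault in a headline result: the primary objective is external validation and intervention is a secondary endpoint (3.5.2). Whether the groups differ in discharge pattern, and which rule the training cohort used, cannot be seen here.

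Finally, censoring at last contact is a recognised cautious choice where survival is unverified. That is fair, but it requires that deaths and treatments after last contact are not counted either.

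**Conclusion.** The point holds for the intervention analysis. The written rule makes follow-up depend on outcome, which overstates the non-meningioma death curve and pushes the intervention curve upward relative to a common cut-off on the same data. The net direction for intervention depends on how fully post-discharge treatment is captured.

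The size rests on assumed rates and chiefly on the unknown gap between last contact and data entry: negligible if the gap is short, several points or more if contact ends near discharge. Bias between PS or ACCI groups is possible but is not shown by the documents.

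The missing competing event is a real but minor gap, and its direction assumes that meningioma deaths are censored, which the protocol does not state. The point should be corrected before analysis; it does not touch the primary validation measures.

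**What to change.** 1. Apply one cut-off to deaths, interventions and survivors among discharged patients, set by a rule that does not depend on outcome.
2. Use the date of data entry only where alive and untreated status at that date is positively verified, for example for a whole site with complete vital-status records. The absence of a death entry is not verification; treating it as such adds event-free time that was never observed. Verifying patient by patient according to what was found would bring the fault back.
3. Otherwise, cut all discharged patients at last documented contact and count no later death or intervention.
4. Make death from any cause before intervention the competing event.
5. Add fields for the date of last contact and the date of SRS or fRT treatment, which the form as shown lacks, and collect Dead/Alive status for rescanned patients too.

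The cost is a few sentences in 3.10.1 and a small change to the form. Data-entry date, date of death and cause of death are already collected. Under step 3 some late events are lost, and the late part of the curves will be less precise.
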